A community-based researcher will educate women about sexual health and cervical cancer by using the materials that will be developed by the ELEVATE team. In addition, women will receive information about self-sampling and will be instructed by the community-based researcher on how to take a self-sample using an illustrative cartoon. Women will then be asked to take a sample on-site. The researcher will collect all samples and bring them to the laboratory of UZ Ghent for analysis by an HPV test (yet to be decided which one). Sample analysis is expected to take 2 weeks time. Women who tested positive for HPV will receive a follow-up phone call to notify their result and will again be informed about cervical cancer screening (pap smear) and about where they can obtain these services; they will receive a contact number to make an appointment as well as information on how to reach the place of the consultation.

Outcome measures that will be examined for arm 3 are:

- Participation rate (i.e., women invited/women who attend the session)
- Knowledge, willingness and uptake of cervical cancer screening prior to the session
- Acceptability of self-sampling
- Uptake of the self-sampling test (women who attend the session/women who take the self-sample)
- Attitudes towards self-sampling (reasons to accept/decline the self-sample; advantages and disadvantages versus conventional screening)
- User experiences among those who took a self-sample (easy/difficult; painless/painful; trustworthy/untrustworthy; etc.)
- Uptake of cervical cancer screening through standard services:
 - A 3-month follow up is proposed to check whether the woman made/went to the appointment
- Knowledge of as well as willingness to get screened for cervical cancer screening will also be assessed during the 3 month follow-up phone call
- Feasibility and cost of the intervention

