3.2. Specific objectives

Objective 1: Assess and compare **attendance rates** following invitation to participate to the study

Hypothesis 1.1: Attendance will be higher when women are offered self-sampling compared to when women are only offered an educational session.

Objective 2: Evaluate the current **knowledge, willingness and uptake** of cervical cancer screening among participants of the acceptability study (arm 2 & 3); assess knowledge improvement and willingness to get screened 3 months after the intervention

Hypothesis 2.1: Knowledge and willingness to get screened will be poor and uptake of cervical cancer screening among the participants will be lower than the national average (but similar to results found in arm 1)

Hypothesis 2.2: After the information sessions, women will be able to link cervical cancer with HPV and will understand the benefit of screening; willingness to be screened will have increased

Objective 3: Assess **attitudes towards and users' experiences** of the HPV self-sampling test among hard-to-reach women (i.e. participants in arm 3)

Hypothesis 3.1: Attitudes towards on-site HPV self-sampling will be overall positive

Hypothesis 3.2: Women who use the self-sampling tool will have positive users' experiences related to the self-sampling device.

Objective 4: Compare the uptake of the on-site HPV testing (arm3) with the current national screening services (arm1) and with off-site referrals (arm2)

Hypothesis 4.1: Uptake of on-site HPV self-sampling will result in an increase in screening coverage compared to standard practices. (arm 3 vs arm 1)

Hypothesis 4.2: On-site HPV self-sampling will have higher uptake than referrals to off-site screening. (arm 3 vs arm 2)

Hypothesis 4.3: Referral to off-site screening following participation in an educational session on cervical cancer will result in higher screening coverage compared to current practices. (arm 2 vs arm 1)

Hypothesis 4.4: Uptake of off-site screening among those who refuse the self-sampling in arm 3 will be lower than uptake of off-site screening in arm 2

Objective 5: Examine the impact of HPV self-sampling on follow-up testing and care

Hypothesis 5.1: Women whose on-site HPV testing came out positive will go for follow-up testing and care

Objective 6: Assess the **feasibility** of the information session and the self-sampling test

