4.1. Study setting/context

Organizations and community-based associations working with socio-economically vulnerable women will be invited to participate. These organizations will be randomly allocated to invite women to either arm 2 or arm 3.

We aim to link the information sessions of the acceptability study to group activities that are offered by the organizations. This was suggested by the community health workers during the focus group discussions as a good way to motivate women to participate. It was reported that it is difficult to gather women for the sole purpose of an information session about their health (especially about cervical cancer that is often not known) and that linking it to an activity for which they are gathered will increase the participation rate.

We are paying attention that organisations and their catchment areas are not too close to each other to avoid spillover.

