4.3. Recruitment of participants

In agreement with the participating organizations, the research team (including the community-based researchers) will hand out invitations (leaflets) to invite women to informative sessions on cervical cancer screening. While handing the invitation, the researcher will shortly describe the goal of the session, emphasizing the benefits for the women. If women are invited for arm 3, they will also be told that they will be offered a self-screening test during the session. Women will receive a leaflet stating the time and place they are expected. Women will be asked to invite other women as well.

We aim to link the sessions to group activities where women are already gathered such as sport activities, integration programs and meals in social restaurants. Therefore, we will work closely with the social

workers and volunteers active in the organizations and will ask for their support to invite women. However, we expect that their contribution will be limited due to their day-to-day workload and tasks.

We will explore with the respective organizations what the best approach is in their context with regard to the timeframe between the invitation and the information session. We learned during the focus group discussions that for many socio-economically vulnerable women it is difficult to commit to show up on another day, for various reasons. Therefore, we aim to organize the educational sessions directly following their group activity, integration class or meal in the restaurant (i.e. the moment they will be invited). In some subgroups of women, such as young mothers, it seems advisable to inform them that they will need to stay a bit longer so they can organize this.

All participants will be offered a small incentive for study participation, such as a voucher.

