6.1. Quantitative data

The primary endpoint is the participation in screening which is defined in Arm 1 as the proportion of women who had a PAP smear taken by a GP or gynaecologist within the national screening program, in Arm 2 as the proportion of women who go for PAP smear after attending the information session with targeted referrals for off-site screening and in Arm 3 as the proportion of women who accept to take an HPV self-test on site after the information session.

Two important measures of take-up will be estimated:

Take-up 1 - To compare the take-up of an on-site HPV screening intervention with the current national screening services accounting for self-selection of women who decide to attend clinics (arm 1 vs. arm 3).

Take-up 2 - To compare the take-up of an on-site HPV screening intervention with targeted referrals to off-site screening (population impact regardless of self-selection) (arm 2 vs. arm 3).

Sample calculation was defined according to an estimated increase in take-up compared with current screening coverage for each study country.

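### Section 6.1 labels Take-up 2 a population impact unaffected by self-selection, but writes no denominator, and the protocol points to session attendees, who choose to come after allocation

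*Protocol*

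**What the plan says.** **Label.** Section 6.1 names two measures. Take-up 2 compares the on-site intervention with "targeted referrals to off-site screening (population impact regardless of self-selection) (arm 2 vs. arm 3".

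**Endpoint.** The same section defines participation in screening "in Arm 2 as the proportion of women who go for PAP smear after attending the information session" and "in Arm 3 as the proportion of women who accept to take an HPV self-test on site after the information session". Neither is written as a ratio.

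**Likely base.** The arm 3 outcome list in section 3.1 gives "Uptake of the self-sampling test (women who attend the session/women who take the self-sample" (the ratio is printed upside down, but its two terms are attendees and takers). Sections 4.6 and 5.2.2.4 collect Pap smear uptake from participants, by a phone call at 3 months. The number invited, counted as leaflets, appears as a denominator only for the participation rate (sections 3.1 and 5.2.1).

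**Order of events.** Section 4.1: "These organizations will be randomly allocated to invite women to either arm 2 or arm 3". Section 4.3: "If women are invited for arm 3, they will also be told that they will be offered a self-screening test during the session". Hypothesis 1.1 in section 3.2: "Attendance will be higher when women are offered self-sampling compared to when women are only offered an educational session".

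**Arm 3 follow-up.** Section 4.6 limits the Pap smear question in arm 3 to HPV-positive women. Hypothesis 4.4 states: "Uptake of off-site screening among those who refuse the self-sampling in arm 3 will be lower" than in arm 2. Section 3.1 lists standard-service uptake for arm 3 without that limit, and section 5.2.2.4 applies the follow-up questionnaire to both arms.

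**The concern.** Allocation is made by organisation. Whether a woman comes to the session is decided afterwards and, in arm 3, with knowledge of the self-test offer. The protocol itself predicts that this offer will change attendance. If the base is attendees, the two groups may differ in who they are as well as in what they were offered. Random allocation of organisations does not remove that difference.

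The label then tells the reader the opposite of what the data can show, and does so for the only randomised comparison of the primary endpoint. Attendance by arm is reported under Objective 1, so an imbalance in numbers would be visible, but not who the additional attendees are.

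The follow-up conflict is a separate matter. If section 4.6 is followed literally, women who declined the self-sample are not asked about a Pap smear, and Hypothesis 4.4 cannot be tested.

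**Working it through.** The protocol states no rate, sample size or power for Take-up 2, so there is no figure to reproduce. **Every rate below is an assumption.**

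**1. Selection alone, attendee base.** Of the women invited, 40% attend under either arm and 30% of them are screened, whichever the arm. A further share s attends only in arm 3 and is screened at rate p. Being in arm 3 changes no attending woman's uptake.

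- Arm 2 attendees: 0.30.
- Arm 3 attendees: (0.40 × 0.30 + s × p) / (0.40 + s).
- s = 0.20, p = 0.10: 0.14 / 0.60 = 0.233, contrast -6.7 points.
- s = 0.20, p = 0.90: 0.30 / 0.60 = 0.500, contrast +20.0 points.
- s = 0.05, p = 0.10: 0.125 / 0.45 = 0.278, contrast -2.2 points.
- s = 0.05, p = 0.90: 0.165 / 0.45 = 0.367, contrast +6.7 points.
- s = 0, or p = 0.30: contrast 0.

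**2. Same women, invited base, s = 0.20.** Arm 2: 0.40 × 0.30 = 12.0%. Arm 3: 0.12 + 0.20 × p, which is 14.0% (p = 0.10) to 30.0% (p = 0.90). The difference is +2.0 to +18.0 points, and it is the true effect if the additional women go unscreened when they do not attend. At p = 0.10 the attendee contrast (-6.7) then has the wrong sign.

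**3. Limits of the invited base.**

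- *Pap smears in non-attenders are not observed.* If the additional 20% would have had one at rate b without attending, the per-invited difference favours arm 3 by 0.20 × b: 1.0 to 2.0 points for b = 5 to 10%. If b = p, the true effect is 0 and the whole 2.0 to 18.0 points is error.
- *Women not reached at 3 months.* Section 5.2.2.4 allows up to five contact attempts. The arm 2 outcome depends on that call, whereas the arm 3 self-sample is seen on site. If unreached women count as unscreened, 12.0% becomes 0.12 × 0.80 = 9.6% at 20% loss and 0.12 × 0.60 = 7.2% at 40% loss. This favours arm 3 by 2.4 to 4.8 points.
- *Onward invitations.* Section 4.3 asks women to bring others, who hold no counted leaflet. If they add 10 to 30% to the arm 3 numerator only, 30.0% reads as 33.0 to 39.0%.
- *Eligibility.* Section 9.4 checks it at consent, after leaflets are given out, so the count may include women outside the criteria of section 4.2.1.
- *Who is invited.* The team handing out leaflets knows the arm (section 4.3), so the invited group is itself formed after allocation.

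**The case against.** The strongest reply is that section 6.1 writes no denominator. The label could itself name the base, meaning all women offered the intervention, and the registers needed for it are collected (section 5.2.1) and entered in the database (section 7). Under Take-up 1, self-selection refers to the decision to attend clinics, so the phrase may mean only that this choice is not conditioned on. An analysis plan not shown here could settle the matter. **What stands:** the contradiction depends on the attendee reading and is not proved. But that is the reading the endpoint wording and the sections cited best support. Even with the narrow meaning of self-selection, a contrast of attendees is not a population impact.

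Sessions held straight after existing activities (section 4.3) should limit additional attendance. The sign reversal also needs women drawn by the self-test to accept it at a third of the common attendees' rate (10% against 30%), which is an unlikely corner. Both points stand; they shrink the probable size but do not support a claim of no self-selection.

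Three stronger readings are tempting and are not supported:

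- *The comparison favours arm 3.* The documents give no rates, and the illustration runs both ways.
- *Randomisation protects the invited women.* Inviters know the arm, so an invited base reduces selection without removing it.
- *Pap smears among arm 3 decliners belong in the primary endpoint.* Section 6.1 and Hypothesis 4.2 define arm 3 by the on-site self-sample. A composite would answer a different question, and the label problem does not require it.

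**Conclusion.** The concern holds in a limited form. The Take-up 2 label is not supported by the comparison most naturally read from the protocol, because attendance is chosen after allocation, in arm 3 with knowledge of the offer, and is expected to differ by arm. An attendee contrast may be biased in either direction.

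No size can be derived from the protocol. With 40% common attendance, 30% uptake and 5 to 20% additional arm 3 attendance, selection alone gives at most -6.7 to +20.0 points; with no additional attendance it gives none. The finding rests on the unwritten base being attendees. If the sponsor intends invited women, section 6.1 still has to say so, since the two bases can give different answers.

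The conflict between section 4.6 and Hypothesis 4.4 is real but narrower: one parenthesis is out of line with sections 3.1 and 5.2.2.4. A reader might infer that the data will not be collected; the documents disagree on this and do not settle it. Overall this should be fixed, with medium confidence.

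**What to change.** **Section 6.1.** Keep the arm-specific endpoints (arm 2: Pap smear by the 3-month call; arm 3: self-sample taken). Define Take-up 2 as that number divided by women invited according to the participation register, compared by organisation as randomised. Report uptake among attendees as a secondary measure without the label. State these limits:

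- the invited base reduces selection but does not remove it, because inviters know the arm;
- leaflets miss women invited by other women and may include ineligible women;
- Pap smears in non-attenders are not observed;
- arm 2 women not reached at 3 months need a sensitivity range, since counting them as unscreened favours arm 3.

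**If this is not adopted,** delete the label and state that Take-up 2 applies to session attendees and is not protected by randomisation.

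**Section 4.6, separately.** Reconcile it with Hypothesis 4.4 and sections 3.1 and 5.2.2.4, so that Pap smear uptake is also asked of arm 3 women who declined the self-sample. Report it for Hypothesis 4.4 and, at most, in a sensitivity analysis of Take-up 2.

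**Cost.** One definition with its limits in section 6.1, one line in section 4.6, and one follow-up question for arm 3 decliners; the registers already exist. Per-invited proportions will be lower than attendee proportions. Dropping the label instead costs one sentence.

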6.2. Qualitative data

Audio recordings of the interviews will be transcribed, and the transcripts will be analysed through content analysis. This technique allows the data to be systematized in key topics and organized in different categories and sub-categories. Simultaneously, written notes taken during the interviews will be also used to improve and complete the information if considered relevant.

7. Data management

All data will be entered in a Redcap. In total, the following information will be entered:

- 1) Participation registers
- 2) Self-administered questionnaire among all (KAP)
- 3) 2 self-administered questionnaire in arm 3 (attitudes towards (=pre-intervention) and users' experience (=post-intervention))
- 4) Telephone questionnaire (=follow-up assessment)

The unique identifier code will be used to link all the questionnaires of the same participant and to ensure pseudonymization of the data.

Only members of the research team will have access to the pseudonymized data: the data will be saved on work computers of team members only, and a back-up will be saved on a protected server that can only be accessed with a username and password.

8. Training community-based researchers

Both researchers with a medical background and community-based researchers will be involved in all stages of the study. Researchers with a medical background and medical students (in the broad sense, including students studying medicine, health promotion, biomedical sciences, etc.) will assist during the educational sessions and possibly, after they followed some sessions provided by the main researcher (gynecologist), give the sessions themselves. Community-based researchers including social workers and community (health) workers will equally be involved in all stages of this study; however, their core responsibilities will be participant recruitment, assisting during the educational sessions, assisting during self-sampling and (post) counselling, and data collection (questionnaires).

Both groups of researchers will be provided training. The training will cover: HPV and cervical cancer, screening and diagnosis of cervical cancer, follow up of cervical lesion; research methods for the project and their specific tasks; interpersonal communication skills; appropriate responses to sensitive

information (i.e. how to react to women who share experiences of sexual violence, stigma, ill health, etc.); appropriate communication of results.

A standard training session will be prepared and adapted at each study site to their needs and context. Training materials will also be developed. The training will be carried out through role plays, video projections and pamphlets.

People who are working or volunteering in the organizations will be invited to this training session, however if they will not take an active role during the sessions, this is not mandatory. In case they will assist in recruiting women, they will receive a shorter training about the main goals and methods of the project.

9. Ethics

9.1. Protection of subjects

A patient safety plan was developed in order to ensure protection of (potential) participants, including a stigma reduction programme and strategies to tackle harms and emergencies. The stigma reduction programme provides details on ethics and communication training of the researchers involved in the study.

Importantly, the team will ensure that invitations, education sessions and self-sample taking will take place in a confidential environment that provides both visual and auditory privacy. The data collected will only be available to researchers and no third parties will have access to the data.

In addition, the team will ensure that no coercion can be exercised on (potential) participants, by ensuring that participation in the study is voluntary and that refusal to participate in the study will have no repercussion whatsoever. In addition, subjects will be informed that the confidentiality of the data collected in the phone calls and questionnaires is guaranteed.

9.2. Benefits for the participants

No payment will be offered in exchange for participation in the study, which eliminates the risk of coercion for poor subjects who may feel pressured to participate for financial gain. It will be explained to each participant that their information will help us to improve future cervical cancer screening programs.

The only benefit that participants may receive is information regarding cervical cancer and HPV screening, which will probably lead to increased knowledge and awareness. Such information will be provided during the information sessions and/or if participants have additional questions afterwards.

9.3. Confidentiality

To ensure confidentiality of data collected during the phone calls and through the questionnaires, the following steps will be taken:

- Only the person who is the community-based researcher (healthcare professional or community health worker) responsible for the data collection will have access to the information of the link between the unique identifier code and the name and contacts of the participants. Other members of the research team will never have access to any name or contact information of participants.

- Through all steps in the process of data gathering, data entry, data cleaning and data analysis, only research team members and the community-based researchers will have access to the data.
- The results of the study may be published for scientific purposes, but anonymity will be protected at all times and no result will be linked to specific individuals.

To ensure that all team members are aware about the latest data management guidelines, a separate document with details on data security, data storage, data sharing and data preservation will be provided to all partners.

9.4. General consent statement

A written consent form will be asked of all participants, in full compliance with the Declaration of Helsinki. The consent form will be written in simple language at a sixth-grade reading level. The language used in the consent form will be developed in collaboration with medical staff accustomed to share medical information with their patients.

The form will clearly state the objectives of the study and will also include a small screening section that will be used to verify whether or not the approached woman is eligible. When a woman is considered eligible, she will be explained in more detail what is expected from her, i.e. which procedures will take place if she decides to participate.

Only participants with decision-making capacity, that is, they are able to give consent, will be involved in the research. Language and literacy capabilities will be assessed. In case the participant cannot read or write herself, an impartial witness will be asked to join the reading of the consent form (authorized substitute decision maker). The witness will sign the consent form together with the participant. The participant will choose a witness so she can select someone she believes is appropriate and reliable (e.g. another woman from the community – without conflict of interest).

The following topics will be covered in the information sheet of the informed consent:

- Description of the study and its objectives
- To know that participation is voluntary
- To be able to withdraw themselves, their samples and their data from the project at any time
- To know that results can be shared with the participants
- Benefits and risks
- No costs for participants
- To receive assurances that appropriate insurance coverage is in place
- To have confidentiality and privacy protections clearly specified, following national legislations.
- To know of any potential commercial exploitation of the research.
- To know that students might participate in this study as research assistants.

Women will be asked if their data can be used in future research. If they agree, they will be asked to tick the box 'I consent to have my data deposited in pseudonymised form in a trusted repository so it can be used for scientific purposes only'. If they don't tick the box, their data will not be released for further use in other research.

